SC/ST girls will be enumerated and included in the cohort. We will conduct a complete-capture enumeration of all SC/ST girls in all trial sites, therefore, all SC/ST girls will be approached for inclusion in the trial.

Families

All families of SC/ST girls will be included in the cohort.

Sample size

The sample size calculations are based on the four co-primary outcomes:

1. Percentage of those enumerated in 7th standard (the study cohorts) who ENTER into grade 8th
2. Percentage of those in the study cohorts who complete 10th standard
3. Proportion of girls in the study cohorts who are married at end line.
4. Proportion of girls in the study cohorts who experienced first sexual intercourse at end line

The sample size calculations are based on the parameters shown in the table below. The baseline numbers are found in the KSS Karnataka report for 2010-2011, a rural assessment by KHPT in 2013, the district level household surveys (DLHS) from 2007-2008, and the Integrated Biological and behavioral Assessment (IBBA) conducted by KHPT from 2006-2011. Broadly speaking, the expected effect sizes are guided by the aim of the intervention to bring the outcomes among SC/ST girls in-line with all girls. Therefore, we have used the prevalence of the outcomes in these surveys to estimate plausible effect sizes.

Parameter	Notes
Harmonic mean cluster size	This is based on an enumeration carried out in the 225 high schools located in 121 villages by KHPT. Approximately 15 SC/ST girls are available at each school
Refusal/loss to follow-up	Refusal and loss to follow-up are expected to be low, approximately 5-10% (14 girls per cluster is used in the calculation, multiplied by 2 to account for the two cohorts)
Between cluster variation (k)	The between cluster variation in the outcomes is not known. Therefore, we have reported sample sizes for a range of values.
Control arm proportions	

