
 1. Proportion transitioning 7-8th (actualized in terms of the proportion dropping out between 7th and 8th) 2. Proportion completing 10th (actualized in terms of the proportion dropping out between 7th and 10th) 3. Proportion married at end line 4. Proportion sexual intercourse at endline 	
 1. For this we calculate sample size calculations for a range of drop-out proportions, from 9% (the State level drop-out proportion for SC/ST girls only) and 17% (the dropout rate among all girls in Bijapur district. These are conservative estimates since we expect that the effects of being SC/ST will augment the figure for the study districts (figures from SSA Karnataka report for 2010-2011). 2. The rural assessment in selected villages in Bijapur and Bagalkot districts by KHPT 2013 found drop out of 34% among devdasi girls. We have assumed 30-40% drop out before standard 10. 3. The District Level Household Surveys (DLHS-2007-08) collected data on age at marriage and has a reasonable sample size in each district. About 21% of the women aged 18-25 married before the age of 15 years. A higher percent of SC/ST women were married as compared to others (25.9% against 19.3%). Therefore the proportion is likely to be around 25% 4. Data from the IBBA among FSWs conducted in

the district of Belgaum found 44.77% of the FSWs reported their first sex was before the age of 15 years. Given 25.9% of the SC/ST women married before the age of 15 years, the proportion who had their first sex before 15 years will likely be a number above this, but most likely less than 44.7%. The Polling Booth Surveys conducted in the rural areas of these districts in 2011 found that 8% of the unmarried females (15-24 years) had ever had sex, whereas 5.3% of the married females (15-24 years) had sex before marriage in Bijapur district. Therefore the proportion who had sex before 15 years is likely to be a number above 30%. We have assumed a conservative range from 20-35%.

Effect (risk ratio)

The risk ratios are guided by comparisons between the estimates of the outcomes in the SC/ST girls and outcome proportions in all girls.

1. Proportion transitioning 7-8th
2. Proportion completing 10th
3. Proportion married at end line
4. Proportion sexual intercourse at endline

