1. We have reported a range of Risk Ratio minimum detectable effect sizes from 30-40%. This is considered to be the most likely of the outcomes to be influenced by the intervention
2. We have reported a range of Risk Ratio minimum detectable effect sizes from 20-25%. The lower effect size than for outcome 1 reflects the perception that this will be harder to influence with the intervention as the barriers to staying in school increase over time
3. The intervention will target marriage directly through school and home based interventions. Therefore, we aim to decrease the proportion married before 15 by 25-30%.
4. The intervention will target sexual debut directly through school and home based interventions. Therefore, we aim to decrease the proportion married before 15 by 25-30%.

Type 1 error

We have set this at the 5% level

Power

We have set this at the 80% level

Transition from 7-8th Standard

These and further sample size calculations included estimations of variance of between-cluster differences when an unpaired t-test is used for final analysis, on the basis of calculations provided by Hayes and Betnett¹⁹.

Transition from 7-8th standard is considered to be the most likely of the outcomes to be influenced by the intervention, and we have reported a range of minimum detectable effect sizes, with risk ratio of RR= 0.70-0.60.

The detectable effect sizes of RR=0.70-0.60 is assumed on the basis that the intervention aims to bring down the higher dropout rate among SC/ST girls to be in-line with the state average dropout rates among all girls. The *Sarva Shiksha Abhiyan Karnataka Analytical report 2010-11* (Education in Karnataka 2010-11) documents a dropout rate among SC/ST girls during higher primary grades of 9%, compared to 5.6% among all girls in the state (Table 18A). Therefore, the state average for dropout rates from higher primary grades among all girls is 38% less than the dropout rates of SC/ST girls, corresponding to a risk ratio of RR=0.62. Note that the dropout rates of SC/ST girls in transition from standard 7 to standard 8 are not available from the report at district level disaggregates, so we used the state averages for SC girls and all girls. On the basis of this uncertainty, and the event that the intervention is not able to fully bring SC/ST drop out during transition to the average among all girls, we have sized the trial to detect weaker risk ratio of 0.70 under certain, plausible, conditions.

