1-type I	Power	Control p	Cluster Size	% reduction	Intervention p	K	# clusters per arm
0.95	0.80	17%	28	30%	11.9%	0.15	30.4
						0.20	32.7
						0.25	35.6
						0.15	24.9
						0.20	26.7
						0.25	29.1
		33%		11.4%	0.15	40.0	
					0.20	42.3	
					0.25	45.2	
					0.15	32.7	
					0.20	34.5	
					0.25	36.9	
9%	5.9%	35%	28	35%	5.9%	0.15	41.7
						0.20	43.3

¹⁹ Hayes RJ and Bennett S, Simple sample size calculation for cluster-randomized trials, International Journal of Epidemiology, 1999; 28, 319-326

			45.4
		0.25	
			31.3
40%	5.4%	0.15	
			32.4
		0.20	
			33.9
		0.25	

Retention in school

We have reported a range of Risk Ratio minimum detectable effect sizes of RR=0.75-0.70. The lower effect size than for outcome 1 reflects the perception that this will be harder to influence with the intervention as the barriers to staying in school increase over time.

The *Sarva Shiksha Abhiyan Karnataka Analytical report 2010-11* (Education in Karnataka 2010-11) shows a higher dropout rate of SC/ST girls (22.5%) in transition from standard 8 to standard 10 compared to all girls (16.5%) in the state: this transition is an important stage in ensuring retention until the end of standard 10 and is how the 'retention' outcome will be actualized. The minimum detectable effect sizes of RR=0.75-0.70 are assumed on the basis that the intervention aims to bring retention of SC/ST girls in line with with the state average among all girls. The ratio between SC/ST girls and all girls of the dropout rates during transition from standard 8 to standard 10 is 0.73. This ratio is used as a indicator for the plausible effect of the intervention on retention to standard 10.

1-type I	Power	Control p	Cluster Size	% reduction	Intervention p	K	# clusters per arm			
0.95	0.80	40%	28	20%	32.0%	0.15	28.3			
						0.20	33.9			
						0.25	41.2			
		23%		30.8%	0.15	21.3				
					0.20	25.5				
					0.25	30.8				
		0.95		0.80	30%	28	20%	24.0%	0.15	38.8
									0.20	44.4
									0.25	51.7
23%	23.1%		0.15		29.1					
			0.20		33.3					
			0.25		38.6					
0.95	0.80		20%		28		23%	15.4%	0.15	44.8
									0.20	48.9
									0.25	54.2
		25%	15.0%	0.15		37.7				
				0.20		41.1				
				0.25		45.5				

Proportion married before age 15

The intervention will target marriage directly through school and home based interventions. Therefore, we aim to decrease the proportion married before 15 by 25-30%, corresponding to risk ratios of RR=0.75-0.70.

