The *District Level Household Surveys (DLHS-2007-08)* collected data on age at marriage and has a reasonable sample size in each district. About 21% of the women aged 18-25 married before the age of 15 years. A higher percent of SC/ST women were married as compared to others (25.9% against 19.3%). Therefore, bringing the proportion in-line with all girls would result in a risk ratio of 0.75.

1-type I	Power	Control p	Cluster Size	% reduction	Intervention p	K	# clusters per arm		
0.95	0.80	35%	28	25%	26.3%	0.15	20.8		
						0.20	24.3		
						0.25	28.7		
		28	30%	24.5%	0.15	14.4			
					0.20	16.7			
					0.25	19.6			
		0.95	0.80	30%	28	25%	22.5%	0.15	24.6
								0.20	28.0
								0.25	32.4
28	30%			21.0%	0.15	16.9			
					0.20	19.2			
					0.25	22.1			
0.95	0.80			20%	28	25%	15.0%	0.15	37.7
								0.20	41.1
								0.25	45.5
		28	30%	14.0%	0.15	25.8			
					0.20	28.0			
					0.25	31.0			

Proportion having had sexual intercourse before age 15

[figure not shown]
The intervention will target sexual debut directly through school and home based interventions. Therefore, we aim to decrease the proportion married before 15 by 25-30%. This is assumed to be equal to the previous indicator i.e. proportion married.

1-type I	Power	Control p	Cluster Size	% reduction	Intervention p	K	# clusters per arm		
0.95	0.80	35%	28	25%	26.25%	0.15	20.8		
						0.20	24.3		
						0.25	28.7		
		28	30%	24.50%	0.15	14.4			
					0.20	16.7			
					0.25	19.6			
		0.95	0.80	30%	28	25%	22.50%	0.15	34.1
								0.20	37.5
								0.25	41.9

				30%	21.00%	0.15	23.4
						0.20	25.6
						0.25	28.5
0.95	0.80	20%	28	25%	15.00%	0.15	37.7
						0.20	41.1
						0.25	45.5
				30%	14.00%	0.15	25.8
						0.20	28.0
						0.25	31.0

K and the number of clusters

[figure not shown]
We are uncertain about the value of k – the between school variation in the outcomes – and therefore explored the relationship between the number of clusters and the value of K for some central and realistic estimates of the above parameters. The relationship is shown for three different effect sizes: 30%, 33%, 35% for the effect on transition from 7-8th standard, and 20%, 23%, 25% for the retention until 10th standard. The power is 80%, type 1 is 5%, number of girls per cluster is 14 (accounting for loss to follow-up), and the proportion in the controls is 13% and 30% for transition and retention, respectively. We have included 34 clusters per arm as the reference line.

[figure not shown]

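### The marriage risk ratio of 0.75 is not the all-girls ratio it is called (that is 0.81), six sexual-debut table cells contradict their labels, and outcomes 3 and 4 carry two definitions

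*Protocol*

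**What the plan says.** **Effect-size rationale.** The Sample size section sets the general rule: "the expected effect sizes are guided by the aim of the intervention to bring the outcomes among SC/ST girls in-line with all girls". For marriage, the section on the proportion married before age 15 gives an overall survey figure ("About 21% of the women aged 18-25 married before the age of 15 years") and then the split by caste, in per cent: "A higher percent of SC/ST women were married as compared to others (25.9% against 19.3". From these it concludes: "Therefore, bringing the proportion in-line with all girls would result in a risk ratio of 0.75". For transition to 8th standard the comparison is "9%, compared to 5.6% among all girls in the state". For retention: "The ratio between SC/ST girls and all girls of the dropout rates during transition from standard 8 to standard 10 is 0.73".

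**Tables.** The marriage and sexual-debut tables each have blocks for control proportions of 35%, 30% and 20%, with 28 girls per cluster, reductions of 25% and 30%, and k of 0.15, 0.20 and 0.25. The protocol says the debut effect is taken to equal the marriage effect. In the 30% block the marriage table prints 24.6/28.0/32.4 and 16.9/19.2/22.1 clusters per arm. The debut table prints 34.1/37.5/41.9 and 23.4/25.6/28.5.

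**Outcome definition.** Outcome 4 appears in both co-primary lists (Outcomes; Sample size) as "Proportion of girls in the study cohorts who experienced first sexual intercourse at end line", and outcome 3 is likewise marriage at end line. Analysis of primary outcomes refers to marriage at the end of the study period. The Summary (Study design) instead speaks of marriage before age 15. The sizing of both outcomes, including section headings, control rates and graphs, is for events before age 15. On the marriage control rate the protocol says, in per cent: "Therefore the proportion is likely to be around 25".

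**The concern.** There are three separate faults in the sizing of outcomes 3 and 4.

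1. The marriage effect is justified as parity with all girls, but the number used is the ratio to a different group, one with a lower rate. The effect looks easier to justify than the protocol's own benchmark allows.
2. Two tables with identical inputs give different cluster counts, so at least one is wrong.
3. A co-primary outcome with two definitions leaves open what will be tested. Table 4 shows that both age at marriage and age at first sex are collected, so either version could be computed from the same data after results are known. The control rates also belong to the definition that is not the listed one.

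**Working it through.** **Inputs.** Type 1 error 5% (two-sided is my assumption; it reproduces the other cells), power 80%, m = 28 girls per cluster, k = 0.15/0.20/0.25. The control proportions and reductions are those in the tables. The formula is the Hayes-Bennett unpaired one the protocol cites:

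c = 1 + (1.96 + 0.84)² × [p0(1−p0)/m + p1(1−p1)/m + k²(p0² + p1²)] / (p0 − p1)²

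**Reproducing the protocol's figures.** The formula returns all 18 marriage cells and all 18 retention cells. It also returns all 18 transition cells, where I took control rates of 17%, 13% and 9% because that table's labels are partly broken in the text available. It returns 12 of the 18 debut cells. The six that fail are exactly those labelled 30% control.

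**(1) Risk ratios**

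- Transition, SC/ST against all girls: 5.6/9 = 0.62, as stated.
- Retention, SC/ST against all girls: 16.5/22.5 = 0.73, as stated.
- Marriage, SC/ST against all women: 21/25.9 = 0.81.
- Marriage, SC/ST against others: 19.3/25.9 = 0.745, the printed 0.75.

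The 21% does behave as an overall figure: it is a weighted mean of 25.9% and 19.3% with an SC/ST share of (21 − 19.3)/(25.9 − 19.3) = 26%.

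Consequences for k = 0.15/0.20/0.25. Power is Φ(√[(c−1)(p0−p1)²/V] − 1.96), where V is the bracketed term and c = 40.

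| Contrast | Clusters needed, m = 28 | Power at 40, m = 28 | Power at 40, m = 26 |
|---|---|---|---|
| 25.9% to 21% (all women) | 51.0/57.3/65.5 | 70%/64%/59% | 67%/62%/57% |
| 25% to 18.75% (25% reduction) | 29.8/33.2/37.7 | 90%/87%/82% | 89%/85%/80% |

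The m = 26 column is included because the summary of the sample size results enrols 13 girls in each of two cohorts, while the tables use 28.

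**(2) Debut cells at 30% control**

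For a 25% reduction and k = 0.15, p0 = 0.30 and p1 = 0.225:

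- p0(1−p0)/28 = 0.00750
- p1(1−p1)/28 = 0.00623
- k²(p0² + p1²) = 0.00316
- c = 1 + 7.85 × 0.01689/0.075² = 24.6

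| Reduction | Printed | Formula (and marriage table) | Excess |
|---|---|---|---|
| 25% | 34.1/37.5/41.9 | 24.6/28.0/32.4 | 9.5/9.5/9.5 |
| 30% | 23.4/25.6/28.5 | 16.9/19.2/22.1 | 6.5/6.4/6.4 |

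The section on K and the number of clusters gives an independent check. It says that debut needs fewer than 34 clusters for a 25% reduction when K is below 0.26. At 30% control the formula reaches 34 at K = 0.266, which agrees. The printed cells already exceed 34 at k = 0.15.

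The origin of the wrong cells cannot be established. A 22% control rate with 28 girls gives 34.1/37.5/41.9, but 30% control with about 18.7 girls gives nearly the same values.

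**(3) Definitions.** The Summary follows girls to about 16. Table 3 runs from May 2013 to February 2017 and from May 2014 to February 2018, about 3.75 years from roughly age 13. Ever married by end line and married before 15 are therefore different proportions. The first cannot be smaller than the second.

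The protocol gives no end-line rate. If it were 30% to 35% instead of 25% (my assumption), a 25% reduction at k = 0.20 would need 28.0 to 24.3 clusters instead of 33.2.

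**The case against.** **Comparator.** Parity is described only as a broad guide, and the 25% to 30% marriage reduction has a second stated reason, that the intervention targets marriage directly. Transition was itself sized at 0.70 when parity was 0.62. The protocol never claims 80% power for a marriage ratio of 0.81; its closing power statement covers only transition and retention. So the 59% to 70% is not a shortfall against a promise. That stands. But for transition the departure from parity was towards a weaker effect, whereas here 0.75 is stronger than 0.81, and the sentence as written is wrong.

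**The reassuring figure.** No marriage table row uses the 25% control rate. The graph text for marriage (more than 34 clusters once K exceeds 0.13) fits about 21.5% control, where 42.8 clusters are needed at k = 0.25, more than the 40 available. This is fair: the 82% to 90% power depends on the 25% rate named in the parameter table.

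**Debut cells.** They err upward, cost no power and did not set the trial size; the 40 per arm is 34 plus 6 added for contamination. Agreed.

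**Definition.** The section on sampling of the adolescent girls says that most or all girls will have reached 15 by follow-up, which may explain the before-15 rates as a proxy. For a relative reduction the proxy is conservative. It does not make the two outcomes the same, and the Summary still names the unlisted one.

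**Conclusion.** All three points hold. The 0.75 is a ratio to non-SC/ST women; parity with all women is 0.81, for which 40 clusters per arm give 59% to 70% power at 28 girls per cluster (57% to 67% at 26). This affects the justification only, because the marriage table is correct for the reductions it states. Six debut cells are too high by about 9.5 and 6.5 clusters per arm, which is harmless to power. The third point carries the most weight: two co-primary outcomes are listed one way and sized another. The consequence for power is probably favourable, but which outcome is to be tested must not be left open. The figures assume a two-sided 5% test, the cited formula and k between 0.15 and 0.25.

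**What to change.** 1. In the marriage rationale, name the comparator as non-SC/ST women (ratio 0.75). If all girls is to remain the benchmark, restate the ratio as 0.81 and report the 59% to 70% power for it at 28 girls per cluster.
2. Replace the six debut cells at 30% control with 24.6/28.0/32.4 and 16.9/19.2/22.1. The graph text supports 30%; if another control rate was meant, correct both the control and the intervention proportions in those rows.
3. Use one definition of outcomes 3 and 4 throughout. End line already stands in both outcome lists and, for marriage, in the analysis section. If it is kept, align the Summary and the sizing headings, give control rates for that definition, and report the before-15 versions as secondary if they are wanted.

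These are text and table corrections, with no change to clusters, recruitment or data collection. The one cost is that keeping the all-girls benchmark makes the marriage rationale less favourable.

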The graph on the left shows that for all values of K we will require more than 34 clusters per arm to detect an effect of 30%. A 33% reduction in the number of girls not transitioning from 7-8th standard will be detectable 80% of the time when K is less than 0.2. For all values of K up to 0.3 34 clusters per arm will be sufficient to detect an effect of 35%.

The graph on the right shows that for values of K above 0.1 the study will require more than 34 clusters to detect a risk ratio of 20% in the retention to 10th standard outcome. A 23% reduction will be detectable 80% of the time when K is less than 0.2. For values of K up to 0.27 the study with 34 clusters per arm will be able to detect a risk ratio of 25% with 80% power.

Married <15yrs

Sex intercourse <15yrs

[figure not shown]

The graph on the left shows that for all values of K more than 0.13 we will require more than 34 clusters per arm to detect an effect on age of marriage of 25%. A 30% reduction in the proportion of girls married before 15 will be detectable 80% of the time when K is less than 0.3.

The graph on the right shows that for values of K below 0.26 the study will require fewer than 34 clusters to detect a risk ratio of 25% in the proportion having sexual intercourse before aged 15.

Cluster size – loss to follow-up and refusal

We show here how the sample size is affected by a reduction in the number of girls in each cluster. These analyses are shown to give a ‘lower bound’ for acceptable levels of loss to follow-up. These are calculated with a risk difference of 35% for transitioning and 23% for retention to 10th standard.

The graph on the top-left shows that between 22 and 27 girls per cluster will be required to be followed up to ensure that there is 80% power to detect a risk ratio of 35% between proportion transitioning from 7th to 8th, depending on the value of K. The graph on the top-right shows that for lower values of K we will require follow-up of an average of at least 22 girls per cluster to detect differences in retention to 10th standard, but that for higher levels of K the requirements for follow-up are more severe. The lower left and lower right graphs show the equivalent calculations for marriage before 15 and sexual intercourse before 15, respectively.

Summary of the sample size calculation results

The study will have 40 clusters per arm.

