There will be 13 girls, on average, enumerated for each of two sequential cohorts in each intervention and control cluster. In effect, 26 girls will be enrolled in each cluster, 1 year apart, corresponding to a total sample of 1050 girls in the control arm and 1050 girls in the intervention arm. We assume that there is minimal loss to follow-up and that 28 girls are followed-up at the endline. With these data we will have 80% power to detect a ratio of around 33% for the transition from 7-8th standard and a 25% ratio for retention until 10th standard. We have included conservative estimates of the control outcome proportions, and reported calculations for a range of K from 0.1 to 0.25.

In order to measure the medium- and short-term outcome indicators for families, the families of the SC/ST adolescent girls recruited in both arms will be interviewed. To facilitate intervention at the family level, each SC/ST adolescent girl in both the arms will be profiled and the main decision maker will be identified. These decision makers will form the sampling frame to recruit the respondents at the family level.

The sample sizes for the girls are summarized in Table 3.

Table 3: Summary of sequential cohort study design

	May 2013	May 2014	February 2017	February 2018
Intervention site, cohort 1	525 girls completed 7 th standard and their families		Follow-up interviews	
Control site, cohort 1	525 girls completed of 7 th standard and their families		Follow-up interviews	
Intervention site, cohort 2		525 girls completed 7 th standard and their families		Follow-up interviews
Control site, cohort 2		525 girls completed 7 th standard and their families		Follow-up interviews

Allocation of clusters to intervention and control arms

68 villages were selected using systematic random sampling from the sample frame of 121.

[figure not shown]
Schools were allocated randomly to either receive the intervention immediately (experimental condition) or at a later date (waitlist control group). The villages were randomised into intervention and control arms so that 34 villages (62 high schools) in intervention and 34 villages (63 high schools) in control arms. This was done by initially selecting 34 villages randomly from the selected 68 villages using STATA 11. These selected 34 villages were allocated into intervention arm and the remaining 34 villages were allocated into control arm.

Accounting for potential contamination

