After allocating the villages to intervention and control arms, there were 12 villages where there was a possibility of contamination because these villages were contiguous with a village in a different arm of the study. To compensate for potential loss of statistical power due to contamination we therefore selected an additional 12 villages (6 intervention and 6 control arm) for inclusion in the study as follows: Of the 53 villages remaining in the sampling frame, we excluded 24 due to their close proximity to villages which had already been selected for the study. From the remaining 29 villages in the sampling frame, an additional 12 villages (6 intervention arm and 6 control arm) with 19 high schools (9 intervention arm and 10 control arm) were randomly selected to be included in the study.

Thus a total of 80 villages (40 in each arm) with 144 high schools (71 intervention arm and 73 control arm) will be included in the study (see diagram below).

Summary diagram

Data collection

In each of the intervention and control villages, quantitative and qualitative assessments will be carried out, both at baseline and following the intervention, among the target groups listed in Table 1.

Closed-ended questionnaires (used in the sequential cohort studies among adolescent girls and their families) have been developed based on a review of available measurement tools. Questionnaires are in Appendix 2. All instruments will initially be developed in English, translated into *Kannada* (the local language), pretested and piloted and revised, and then back-translated. Tables 4, 5 and 6 provide summaries of the different major domains and sub-domains under each indicator that will be measured in these sequential cohort surveys among the adolescent girls and their parents, respectively.

Table 4: Indicator domains and sub-domains that will be measured in sequential cohort studies of SC/ST adolescent girls in control and intervention villages, using a structured behavioural questionnaire

Major domains	Minor domains
Impact and long-term outcomes	
Demographics	Geographic location, school, age, caste, age at menarche, number of siblings in the family (male and female), parents' living status, their education, occupation, land holdings and household income, whether anyone in the family is a Devadasi/sex worker, and relationship to the adolescent girl

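### Three figures in the sample-size section are wrong as written: 28 girls followed up per village from 26 enrolled, six sexual-debut cells that do not belong to their 30% control label, and a marriage risk ratio of 0.75 credited to the wrong comparator

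*Protocol*

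**What the plan says.** **Cluster size.** The parameter table under Sample size gives the starting point, "Approximately 15 SC/ST girls are available at each school", and the calculation input: "14 girls per cluster is used in the calculation, multiplied by 2 to account for the two cohorts". That makes 28 per cluster, after an allowance of about 5-10% for refusal and loss. The Summary of the sample size calculation results gives 13 girls per cohort, 1050 girls per arm and 40 clusters per arm: "In effect, 26 girls will be enrolled in each cluster, 1 year apart". Table 3 agrees, with 525 girls per arm per cohort. The summary then says "We assume that there is minimal loss to follow-up and that 28 girls are followed-up at the endline" and bases its 80% power claims on those data.

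**Sexual debut.** The section on intercourse before age 15 takes over the marriage effect: "This is assumed to be equal to the previous indicator i.e. proportion married". At 30% control, cluster size 28 and K of 0.15, 0.20 and 0.25, its table prints 34.1, 37.5 and 41.9 villages per arm for a 25% reduction, and 23.4, 25.6 and 28.5 for a 30% reduction. For the same inputs the marriage table prints 24.6, 28.0 and 32.4, and 16.9, 19.2 and 22.1. The commentary on the debut graph says that "for values of K below 0.26 the study will require fewer than 34 clusters to detect a risk ratio of 25" per cent.

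**Marriage.** The survey figures given are about 21% of women married before 15, and 25.9% of SC/ST women against 19.3% of others. The text concludes: "Therefore, bringing the proportion in-line with all girls would result in a risk ratio of 0.75".

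**The concern.** These passages are the protocol's own account of its power for four co-primary outcomes. The follow-up figure in the summary cannot occur, so the power claim attached to it has no valid base. Two tables with identical inputs give different answers, and the debut commentary is hard to square with the debut table, which already prints 34.1 villages at K 0.15 and 37.5 at K 0.20. The wording on marriage tells the reader that catching up with all girls is a 25% reduction, when on the quoted figures it is a smaller one. A sponsor, funder or later author who repeats these numbers will repeat the errors.

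**Working it through.** **Formula.** The protocol cites the standard unmatched cluster-trial formula with between-cluster coefficient of variation K:

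c = 1 + 7.849 × V / (p0 − p1)², with V = p0(1 − p0)/n + p1(1 − p1)/n + K²(p0² + p1²).

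Here 7.849 = (1.960 + 0.842)², taking the 5% error as two-sided. Power = Φ(√[(c − 1)(p0 − p1)²/V] − 1.96).

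**Reproducing the tables.** With n = 28 this gives 66 of the 72 printed counts to one decimal, reading the unlabelled second transition block as 13% control. Example, marriage at 30% control, 25% reduction, K 0.15: V = 0.00750 + 0.00623 + 0.00316 = 0.01689; (0.075)² = 0.005625; c = 1 + 7.849 × 0.01689/0.005625 = 24.6, as printed. The only six failures are the debut rows labelled 30%.

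**1. Cluster size.** 1050/40 = 26.25 enrolled per village; 28 × 40 = 1120 per arm. The value 28 is the table input 2 × 14. The documents do not show which number is wrong. The figure of 15 is per school, and the contamination section has "Thus a total of 80 villages (40 in each arm) with 144 high schools", that is 144/80 = 1.8 schools per village.

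Example at n = 26, transition, K 0.25: p0 = 0.13, p1 = 0.0871, V = 0.00435 + 0.00306 + 0.00153 = 0.00894, (p0 − p1)² = 0.00184. Then √(39 × 0.00184/0.00894) = 2.834 and power = Φ(0.874) = 80.9%.

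Power (%) at K 0.10 / 0.15 / 0.20 / 0.25:

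| Villages per arm | Girls followed up | Transition (13% control, 33% reduction) | Retention (30% control, 25% reduction) |
|---|---|---|---|
| 40 | 28 | 88.8 / 87.5 / 85.6 / 83.2 | 96.8 / 95.0 / 92.0 / 87.7 |
| 40 | 26 | 86.5 / 85.2 / 83.3 / 80.9 | 95.7 / 93.8 / 90.6 / 86.2 |
| 40 | 24.7 (5% loss) | 84.8 / 83.4 / 81.6 / 79.2 | 94.9 / 92.8 / 89.6 / 85.1 |
| 40 | 23.4 (10% loss) | 82.9 / 81.6 / 79.7 / 77.4 | 93.9 / 91.7 / 88.4 / 83.9 |
| 34 | 26 | 80.4 / 78.9 / 76.8 / 74.1 | 92.3 / 89.5 / 85.4 / 80.1 |

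**2. Debut rows.** At a true 30% control the formula gives 24.6 / 28.0 / 32.4 and 16.9 / 19.2 / 22.1, identical to the marriage table. Searching over control rates with n = 28, 22% reproduces all six printed values. Example, 25% reduction, K 0.15: V = 0.00613 + 0.00492 + 0.00170 = 0.01275; (0.055)² = 0.003025; c = 34.1. The overstatement runs from 28.5/22.1 = 1.29 to 34.1/24.6 = 1.39.

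The largest K at which 34 villages detect a 25% reduction with n = 28 is about 0.265 at 30% control and 0.148 at 22%. The debut commentary's limit of 0.26 therefore fits about 30%. The adjacent marriage commentary puts its limit for a 25% reduction at K 0.13. The formula gives 0.115 at 21% and 0.133 at 21.5%, so that graph fits about 21%.

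**3. Marriage comparator.** 19.3/25.9 = 0.745, which is SC/ST women against others. 21/25.9 = 0.811, which is SC/ST women against all. Because 21% is given only as approximate, 20.5-21.5% gives 0.79-0.83.

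**The case against.** **The stronger reading: the case for 40 villages per arm collapses.** A reader might infer this, and the documents do not support it. The graphs use 34 villages per arm as the reference and 34 per arm were randomised first. The other six per arm were added to offset possible contamination, not because a table called for them. At 40 villages and 26 girls both claims in the summary still hold at the stated central control rates. The same history limits the reassurance, however: power at 40 assumes that contamination costs nothing. The protocol does not quantify that cost, so 34 is an illustration and not an estimate.

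**That marriage is underpowered because parity with all women is about 0.81.** This does not follow. The stated target is a 25-30% reduction, the marriage table is correct for it, and parity is offered only as broad rationale. The trial was not sized for 0.81.

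**That the debut commentary proves a 30% control rate.** It does not. The figures are missing from the text at hand, and the text gives graph control rates only for transition and retention. The 30% and 21% above are inferred from the K limits.

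**That the summary hides the 13% control rate behind its transition claim.** It does not: the rate is stated under K and the number of clusters.

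It is also fair to say that the debut error is conservative, since it asks for more villages than the labelled inputs require. None of this removes the three errors.

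**Conclusion.** The point holds as three errors of statement in the sample-size section.

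- Follow-up of 28 from 26 enrolled is impossible. If 26 is right, the cost against 28 at 40 villages is about 2 points of power for transition and about 1 to 1.5 for retention. Transition drops below 80% with 5% loss only at K 0.25, and with 10% loss at K 0.20 and above.
- Six debut cells carry the wrong control label or the wrong values, overstating the requirement by 29-39%.
- The marriage risk ratio of 0.75 is right for non-SC/ST women and mislabelled as parity with all girls.

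The design is not undermined. The conclusions rest on the cited formula with a two-sided 5% level, which reproduces every other printed count, and on reading the quoted 21% as the figure for all women. The power figures also take the central control rates of 13% and 30%.

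**What to change.** 1. Reconcile 13 girls per cohort, 14 × 2 and 15 per school, and restate power at a follow-up no larger than enrolment. If 26 is right, give 81-87% for transition and 86-96% for retention over K 0.25-0.10, labelled as assuming 40 fully effective villages per arm, no contamination and no attrition. Beside them give transition at 77-85% with 5-10% loss, and at 74-80% for 34 villages with 26 girls as an illustrative lower case.
2. In the debut table, replace the six cells with 24.6 / 28.0 / 32.4 and 16.9 / 19.2 / 22.1. Alternatively, relabel them as 22% control with intervention proportions of 16.5% and 15.4%. In either case state the control rates behind the marriage and debut graphs, so that the commentary can be checked against the tables.
3. Name non-SC/ST women as the marriage comparator and keep 0.75.

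The cost is a few sentences and six table cells. Design, number of villages and enrolment stay as they are.
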